2. I felt joyful, glad, happy.
3. I felt in control, coping well, on top of things.
4. I felt sad, downhearted, unhappy.

Scale:

0 = Not at all

1 = A little bit

2 = Somewhat

3 = Moderately

4 =Extremely

Consumption Battery – Evening, last item administered – Supplement

1. Thinking back on how much sugary drinks you had **today**, which is most true for you:

Response options: Assessment 1 (baseline)

- I drank less than I usually do
- I drank about as much as I usually do
- I drank more than I usually do

Response options: Assessment 2 and beyond
(1-month post-Ban and all further assessments)

**SUTTER HEALTH
INSTITUTIONAL REVIEW BOARD**

Protocol Summary Form

- I drank less than I usually did before the Sweet study
- I drank about as much as I usually did before the Sweet study
- I drank more than I usually did before the Sweet study

Self-Efficacy Battery – Morning

If going to work:

1) How sure are you that you will avoid drinking sugary drinks today while at your Sutter Health workplace?

Not sure at all ----- Extremely sure

Sliding bar, slider starting at middle or optimally nowhere and it gets placed when the respondent touches the screen, if starting in the middle then movement of bar required to advance to next question

- Don't know
- I don't plan to go to my Sutter Health workplace today

2) How sure are you that you will avoid drinking sugary drinks today while **not** at your Sutter Health Workplace?

[1] Not sure at all

[2]

[3] Somewhat sure

[4]

[5] Extremely sure

- I do not drink sugary drinks
- Don't know

Blood Draw

The orders for the blood draw will be signed off by [name] the study physician. Results will be sent to patients via My Health Online. The study participants will be asked to review out of range labs with their primary care physician

(4c) Methods of Data Analysis:

Analysis Plan for Aim 1: *How well does each intervention work alone?* We will assess the independent effects of the brief counseling intervention and workplace SSB sales ban on changes in primary and secondary outcomes.

Introduction: Aim 1 analyses will compare primary and secondary outcomes for employees exposed to the brief intervention only, the SSB sales ban only, and no intervention. Our operative hypothesis is that both the brief counseling intervention and sales ban will independently decrease HOMA and waist circumference relative to no intervention. Of four smaller studies testing the effects of brief SSB

**SUTTER HEALTH
INSTITUTIONAL REVIEW BOARD**

Protocol Summary Form

counseling interventions, all found decreases in SSB consumption and BMI.⁴¹⁻⁴⁴ A pilot study and current trial by this team found that workplace sales bans reduce SSB consumption, waist circumference and some blood biomarkers for metabolic disease.¹¹

Analyses for all aims will also consider the hypothesis that those at highest risk for obesity and metabolic disease will benefit more from the interventions. This is justified by our pilot study showing that employees with a baseline BMI <25 benefitted most from the sales ban and brief intervention.¹¹ Preliminary studies (described above) suggest that ethnic minority and lower occupational status employees may experience disproportionate reductions in SSB consumption following an employer sales ban.

Analyses for all aims will also consider the possibility that study participants exposed to the interventions could compensate for reduced SSB consumption during work hours by increasing their consumption of SSBs at home, or by increasing calories from sugary foods or in the total diet.^{107,108} In our evaluation of the UCSF sales ban, we observed no compensatory at-home SSB consumption but rather, spillover effects of the intervention: After 12 months of exposure to a sales ban, the average SSB intake of heavy drinkers not only declined at work but also by 40% at home (by 9.3 oz/day) (data unpublished).

Research Design for Aim 1: The main analysis will focus on ANOVA and regression modeling to determine the independent effects of each intervention on primary and secondary outcomes.

Key Measures for Aim 1: As described in section C3d above: HOMA, waist circumference, abdominal adiposity, SSB consumption, insulin sensitivity, BMI, lipid profile, triglycerides, triglycerides:HDL ratio, liver function, glucose control, demographics, risk factors/disparities, and intervention assignment.

Analytic Plan: We will analyze Aim 1 using all data collected at the baseline, 6- and 12-month time points. First, we will use ANOVA to compare group means and determine whether there is a significant main effect for each intervention (the sales ban and the brief intervention). Based on theory and our previous studies, we know that baseline risk factors and demographics are likely relevant to the impact of these interventions; those at greater baseline risk tend to benefit more from the interventions. Therefore, each dependent variable will also be examined using a linear regression model, which allows us to observe the main effects of these factors. For example, the model predicting HOMA change would include assignment to the sales ban condition (coded as 0/1), assignment to the brief intervention condition (coded as 0/1), baseline HOMA, baseline SSB consumption, baseline BMI, race/ethnicity, and sex. Subsequent models can consider baseline BMI > 25, ethnicity and job classification. The procedure for analyzing each outcome would be the same, but with each primary and secondary outcome substituted for HOMA in turn.

For SSB consumption, we will examine at-work consumption, at-home consumption, and total consumption as separate outcomes to thoroughly investigate the impact of the interventions across work and home environments. We will similarly check for potential compensatory consumption in sugar from calories and total calories for participants in the intervention conditions relative to controls. If ASA-24-based total calories or calories from sugar disproportionately increase in the intervention groups, this suggests a compensatory effect.

Although we believe our strategy of cluster randomization and controlling for individual differences that can vary regionally (such as ethnic distribution) is sufficient, we will also analyze the effects of the brief intervention via an exploratory mixed regression model, with individuals nested within sites, to see if study site was an important factor. If it is, we will consider mixed models where possible.

**SUTTER HEALTH
INSTITUTIONAL REVIEW BOARD**

Protocol Summary Form

Power Calculations: Power calculations are based on changes observed in the pilot study and response rates from the current Sutter Health trial. Calculations are conservative, based on 80% retention of participants after 12 months. With an initial N of 700 drawn from 16 Sutter Health sites randomly assigned to the sales ban and control conditions, and with participants within those sites randomly assigned to brief intervention/no brief intervention conditions, 80% retention would result in an overall N of 550 at 12 months. This results in approximately 138 in each of four experimental conditions: brief intervention + sales ban, the brief intervention only, sales ban only, and no intervention. Power analysis for a full factorial design conducted with the BDEsize¹⁰⁹ package within R¹¹⁰ indicates that with 80% power and an alpha level of .05, we will be able to detect effect sizes as small as .08 for the effect of each intervention on each outcome.

Anticipated Problems and Alternative Approaches: One potential problem is attrition, particularly biased attrition. We have calculated the sample to allow for up to 20% attrition; this is a conservative number based on our current Sutter Health data. In the UCSF pilot, which took place entirely pre-pandemic, we achieved a 94.4% response rate for blood draws. The existing study team has experience with the challenges of retaining a sample of health care workers during a challenging time and can use the same techniques (e.g., email and phone outreach) to reduce attrition here. We will conduct statistical tests to determine if attrition is biased on baseline risk levels, demographic factors (including regional differences), or study condition.

As with all self-report data, the survey data on SSB consumption could be biased, perhaps particularly for intervention participants who want to self-present improvement. However, the anthropometric and blood measures are objective and should show a consistent pattern with the SSB changes. Standard data cleaning procedures should reveal any extreme cases of self-representation bias. For SSB consumption data, we have also established a convention in previous studies of pruning outliers that are more than 4 SD away from the mean to reduce error from participants who may have responded inaccurately.

We have several primary and secondary outcomes. To avoid bias from multiple statistical tests, we will closely examine patterns of data. Many of the biomarkers are related, for example, as are the anthropometric measurements. Thus, it will be apparent whether or not each result is consistent with the overall pattern of health impacts.

Expected Outcomes: We expect statistically significant main effects for both study condition variables in the ANOVA analysis, specifically that the means for each of the three groups exposed to the sales ban and/or brief interventions will demonstrate more improvement (reduction in HOMA, abdominal adiposity, blood lipids, SSB consumption, BMI, etc.) than those in the group receiving neither intervention. We also anticipate statistically significant coefficients for each study condition variable in the regression analysis that again indicates that those interventions are linked to better outcomes. This would indicate that each intervention has an effect.

Analysis Plan for Aim 2: *Does a multilevel intervention work better?* We will assess the multilevel effects of combining a brief intervention and SSB sales ban on outcomes.

Introduction: The goal of Aim 2 is to test the hypothesis that the combined intervention will have a greater effect on outcomes than the brief intervention or sales ban alone. This is justified by our pilot study findings that employees benefitted most from the multilevel intervention (see Figure 1)¹¹ and by

**SUTTER HEALTH
INSTITUTIONAL REVIEW BOARD**

Protocol Summary Form

the socioecological model which argues that obesity prevention should address multiple levels of intervention at once.⁹⁹

Research Design for Aim 2: The analysis will use ANOVA and regression models similar to those above, but with the key addition of an interaction term for the two interventions, allowing us to explore the possibility that they work better in combination than separately.

Key Measures for Aim 2. Measures are the same as those described above under Aim 1.

Analytic Plan for Aim 2: Having established the main effects of each intervention under Aim 1, our analyses for Aim 2 focus on the interaction between them. Specifically, we anticipate that the combined intervention will have an effect above and beyond the simple additive effects of the two interventions. This analysis will require replicating the ANOVA and regression models used for Aim 1 with the addition to each of an interaction term for the two interventions. For example, the model predicting HOMA change will include assignment to the sales ban condition (coded as 0/1), assignment to the brief intervention condition (coded as 0/1), the interaction term for the two conditions (sales ban*brief intervention), baseline HOMA, baseline SSB consumption, baseline BMI, race/ethnicity, job classification (if sample size allows, as above), and sex. The procedure for analyzing each outcome is the same, but with each primary and secondary outcome substituted for HOMA in turn. This time, the main variable of interest will be the interaction term. We will graph and deconstruct each significant interaction term to determine the details of the interaction.

Power Calculations: As with Aim 1 above, power calculations are based on findings from the UCSF pilot and retention rates from the Sutter pilot. We will have 175 participants in each of the following groups. With 80% retention, this allows a final N of 550, with approximately 138 in each of the four experimental conditions. Power analysis for a full factorial design conducted with the BDEsize¹⁰⁹ package within R¹¹⁰ indicates that at 80% power and an alpha level of .05 we will be able to detect effect sizes as small as .12 for the interaction between the two interventions.

Anticipated Problems and Alternative Approaches: As with Aim 1, attrition and self-report bias are the primary potential issues we anticipate; handling of each is described above.

Expected Outcomes: We anticipate a significant interaction term, and more specifically, that the effect of the sales ban and brief intervention together will be stronger than each is individually. Participants assigned to the brief intervention and working at sites with a sales ban would thus demonstrate the greatest amount of change, and more change than one would expect if the effect of the two conditions were simply additive.

Analysis Plan for Aim 3: (Exploratory): *How does the intervention work?* We will test whether changes in SSB craving mediate the effects of the multilevel intervention on outcomes.

Introduction: The goal of this analysis is to examine SSB craving as a mediator in the relationship between the multilevel intervention and primary and secondary health outcomes. This is justified by our pilot study analysis showing that employees with a high level of baseline craving benefited more from the multilevel intervention than comparable employees exposed to the sales ban alone.¹² This study is designed to test the mediation model for the sales ban and brief intervention separately, helping us to understand the “active ingredients” in the multilevel intervention. We can also explore differential benefits for members of high-risk groups.

Research Design for Aim 3: This exploratory analysis will estimate mixed effects using logistic regression models. In contrast to some approaches toward mediation analysis (e.g.,¹¹¹⁻¹¹⁴), ours will

**SUTTER HEALTH
INSTITUTIONAL REVIEW BOARD**

Protocol Summary Form

simultaneously test all paths, including indirect effects through the mediator,¹¹²⁻¹¹⁴ regardless of the presence of a statistically significant total intervention effect.¹¹⁴ Available measures allow us to examine the extent that changes in SSB cravings and SSB consumption after cravings mediate the effects of the multilevel intervention on outcomes.

Key Measures for Aim 3: In addition to measures described above, this aim incorporates text message-based EMA data that captures SSB cravings in the context of day-to-day life.

Analytic Plan for Aim 3: Participants will respond to a question asking if they experienced a craving for SSBs as *yes* or *no*. We will use this SSB craving variable (M), along with group assignment (X), to predict 12-month SSB consumption (Y). This simultaneous mediation model will comprise, first, a mixed effects logistic regression model (Path A in Figure 2 above, from X to M). This model will include random effects for day nested within study period, nested within person for each of the possible reports per day (morning, afternoon, evening, and “any other time not previously reported”). The dependent variable will be the dichotomous primary outcomes reflecting the experience of a craving or whether a craving was acted upon. Model covariates (fixed effects) include time of day, study period, randomization group, and the interaction of study period by randomization group. This will allow us to estimate the odds of having a craving or indulging in one at 6- and 12-months compared to baseline, separately for each experimental arm, as well as allowing for direct comparisons between study arms at each time point.

A second component of the model is a mixed effects linear regression model (Path B in Figure 2 above, from M to Y) that links a change in cravings between baseline and the 6-month follow up (measured as the change in the proportion of responses in which subjects reported cravings) to SSB consumption and HOMA at 12 months. We will perform this mediation model first without covariates¹¹⁵ and then will perform it with other predictors of SSB consumption (e.g., demographics, high-risk group) as in Aim 1. This analysis will allow us to estimate the proportions of variance in SSB consumption at 12 months that are related to changes in SSB craving experiences.

The relationship between the interventions and SSB consumption without the inclusion of craving (Path C) will have already been established in the analyses for Aims 1 and 2, so lastly, we will examine Path C' (interventions predicting consumption and waist change with the inclusion of the craving mediator). This will necessitate a model similar to those used in Aims 1 and 2, but with the addition of craving change and an interaction term for intervention*craving change.

Anticipated problems and Alternative Approaches: This is an exploratory analysis, and thus may not be able to detect very small mediation effects. However, based on our pilot analysis with a much smaller sample, we do not anticipate this will be an issue. The same caveats about retention and self-report bias described in the Aim 1 analysis plan also apply here.

Expected Outcomes: We anticipate that participants in the multilevel intervention group will have a greater reduction in cravings than those in the sales ban or brief intervention groups alone and no intervention groups. We also anticipate that a greater reduction in cravings will be associated with greater reduction in SSB consumption and HOMA at 12 months.

(4d) Subject Selection:

Inclusion Criteria:

1. Full-time employee who works on campus at one of the 16 Sutter Health participating sites.
2. English speaking.

**SUTTER HEALTH
INSTITUTIONAL REVIEW BOARD**

Protocol Summary Form

3. Reports drinking ≥ 3 SSBs/week.
4. Agrees to having two fasting blood draws.

Exclusion Criteria:

1. Pregnant

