To assess the effectiveness of this multilevel intervention, called the workplace *Metabolic Health Improvement Program (MHIP)*, we will conduct a double-randomized trial in partnership with the clinical trials division of a large Northern California-based academic healthcare system, Sutter Health ($N=700$ employees on $N=16$ hospital campuses). We will first cluster-randomize 8 Sutter Health hospital campuses to the SSB sales ban condition and 8 campuses to serve as controls (no sales ban). Across these 16 campuses, we will further randomize heavy-SSB-consuming employees (>30 oz/week) to receive a brief SSB counseling intervention delivered remotely or to a control condition.^{11,12} The **primary outcomes** are central obesity (e.g., waist circumference) and change in serum insulin sensitivity (homeostatic model assessment [HOMA] ratio). **Secondary outcomes** include changes in SSB consumption, Body Mass Index (BMI), and lab values to include: lipid profile, triglycerides, triglyceride:HDL ratio, uric acid, ApoA, ApoB, lactate, ALT/AST, GGT, fasting glucose, fasting insulin, HbA1c. We will assess dietary composition remotely using the Automated Self-Administered 24-hour (ASA-24) at baseline, 6 and 12 months, and waist circumference remotely with empirically validated instructions and a standardized tape measure provided to participants. We will collect blood samples in the workplace labs at baseline and 12 months. All analyses will consider compensatory changes in at-home SSB intake, calories from sugar, and total calories. Aims are:

Aim 1: How well does each intervention work alone? We will assess the independent effects of the brief counseling intervention and workplace SSB sales ban on changes in primary and secondary outcomes. We will compare outcomes across employees exposed to the brief intervention only ($n=175$), SSB sales ban only ($n=175$), and no intervention ($n=175$). *We hypothesize that the brief counseling intervention and sales ban will each independently decrease waist circumference and HOMA relative to no intervention. Those at high risk (baseline BMI >25 , ethnic-minority, and lower-occupational status) will benefit more from the interventions.*

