Public health impact: If effective, the proposed employer-sponsored multilevel intervention will offer an efficient, scalable strategy for preventing obesity in millions of American working adults. This study will also contribute to science on mechanisms of change in obesity prevention and inform the design of interventions that exploit synergies between individual behavior change strategies and food environment policies.

4. METHODS:

(4a) General Study Design:

This is a prospective, double-randomized study in which 16-Sutter Health affiliate hospital campuses will be cluster randomized to control (no SSB sales ban) vs. intervention (removal of SSBs). Across these 16 campuses, we will enroll 700 employees and then randomize those who self-report consuming >30 oz of SSB per week to receive a brief counseling intervention or control (no intervention).

**SUTTER HEALTH
INSTITUTIONAL REVIEW BOARD**

Protocol Summary Form

(4b) Procedures:

Cluster Randomization of 16 Sutter Health Affiliates

Sutter Health affiliates will be eligible to participate in the study who meet the criteria: 1) the affiliate has not participated in a SSB intervention; 2) the affiliate is not in a county that has instituted a SSB sales tax. Affiliates will be stratified by their location (urban vs. rural) and number of employees and will be randomly assigned using a computer program to be assigned to either control or intervention. Sutter Health leadership ([name] and [name]) have signed a letter of support to conduct this study.

Sites randomized to the SSB will eliminate sugar-sweetened beverages from the cafeterias, vending machines, Walgreens, vendors, and from patient care areas. Sutter Health has already implemented Healthy Beverage Initiatives (HBI) at Alta Bates, Palo Alto Medical Foundation (PAMF) and all CPMC campuses.

Study Procedure	Description	Baseline	6 Months	12 Months
Informed Consent	Procedures Described Below	X		
Demographics	Self-reported gender, ethnicity, household income, education, work location, hours, shifts	X	X	X
Medical History	Self-reported concurrent medications and general medical history with an emphasis on diabetes	X	X	X
Height	Measured using a stadiometer on a standardized scale at a semi-private location on the affiliate campus.	X		
Weight	Obtained on a standardized scale at a semi-private location on the affiliate campus.	X	X	X

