Waist Circumference	A tape measure with instructions will be provided to the participant to measure at the designated timepoints.	X	X	X
Fasting Blood Draw	The collection will include: complete metabolic and lipid panel, uric acid, ApoB, GGT, glucose, insulin, HbA1c. These are biomarkers that are risk factors for poor metabolic health, diabetes, and cardiovascular disease	X		X
BevQ	This questionnaire seeks to quantify the frequency, type and volume of beverages consumed at work and home.	X	X	X

**SUTTER HEALTH
INSTITUTIONAL REVIEW BOARD**

Protocol Summary Form

ASA 24	This is a web-based, 24-hour dietary recall tool developed by the National Cancer Institute	X	X	X
Stanford Leisure Time Scale (L-CAT)	This is a scale that measures physical activity.	X	X	X
*PROMIS4a Depression	Assesses the presence and severity of symptoms of depression.	X	X	X
Beverage Craving Questionnaire (FCQ-T-R)	Assesses the following: 1) preoccupation with sweetened beverages; 2) loss of control; 3) positive outcome expectancy; 4) emotional cravings	X		
Reward Based Eating Drive (RED-13)	Assesses three aspects of drive to eat: 1) loss of control; 2) lack of satiety; 3) preoccupation with food	X	X	X
Perceived Stress Scale	This is a widely used questionnaire to assess stress levels. It evaluates the degree to which an individual has perceived life as unpredictable, uncontrollable, and overloading over the previous month.	X	X	X
Copenhagen Burnout Inventory (CBI)	This six-item inventory measures personal burnout experienced by participants.	x	x	x
Self-Efficacy	These questions are used to determine if an individual exhibits intention to reduce SSB consumption.	X	X	X
Science of Behavior Change Texts Parent Grant	Assesses craving, psychological stress, consumption and self-efficacy (two texts/day x four days/week)	X	X	X
Science of Behavior Change Texts Supplemental Grant	Assesses craving, psychological stress, consumption and self-efficacy (two texts/day x four days/week)	Additional texts will be sent at the following time periods: 1, 2, and 3 months after SSB intervention.		
EPIC EMR	Lab results from the blood draw will be extracted from EPIC utilizing the resources of the Center for Health Services Research (CHSR). Limited data from the medical record will be extracted by CHSR that looks at metabolic health.	X		X
Incentive Gift		X	X	X

**SUTTER HEALTH
INSTITUTIONAL REVIEW BOARD**

Protocol Summary Form

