***Patient-Reported Outcomes Measurement Information System (PROMIS):** We have selected a self-report measures of depression which are person-centered which all study participants will be asked to complete. We will investigate the possible correlation between SSB consumption, general health and depression as well as change over time between the intervention and control campuses. Subjects who report high levels of depression will be provided with contact information to Sutter Health's Employee Assistance Program (EAP). No documentation will be placed in the subject's medical or employment record.

REDCap will be set-up with a notification alerting the CRCs when the depression scores result with severe depression. When the participant completes their questionnaires, the Clinical Research Coordinators will review the depression questionnaire. If a participant scores a severe depression (score, a phone call will be made to the participant using a script. A form has been created and will be used as documentation. This includes a script for leaving a message and for a live call. During a live call only, the Clinical Research Coordinator will inform the participant of their high score and will with the phone number to Sutter Health's EAP.

Demographics: Including gender, ethnicity, primary work location, occupational status, income, and usual number of worked shifts each week will be recorded via REDCap.

Medical History: Concurrent medications and general medical history will be obtained directly from study participants with an emphasis on metabolic history such as diabetes. Data will be recorded via REDCap

Height, weight, and waist circumference measurements: Subjects will be asked to record their self-reported height in REDCap. Height and weight will be measured using a standard scale with an attached stadiometer in a semi-private location at the affiliate and record their weight and height in REDCap. A tape measure and instructions on measuring waist will be sent to the participant's home. They will record the measurement in REDCap.

Fasting Blood Draw: A fasting blood draw will take place at the draw station of the local affiliate. Labs will be drawn at baseline and at 12-months. The panels will be comprised of metabolic and lipid panels that pertain to metabolic syndrome. Labs will be accessible to participants using My Health Online.

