Medical Record: Medical record data will be requested for the Sutter EHR (Epic) over a seven-year period (to include one year prior to enrollment, the 12-month study period and for five years thereafter). Data collection will include metabolic parameters related to obesity, such as: lipid panels, glucose, insulin, liver panels, height, weight, and past and prospective history. Medical records data collection will include medication history, progress reports, discharge summaries, and other data allowing us to look at the long-term impact of metabolic health in this population.

Depression: We will investigate the possible correlation between SSB consumption, general health and depression as well as change over time between the intervention and control campuses.

**SUTTER HEALTH
INSTITUTIONAL REVIEW BOARD**

Protocol Summary Form

Benefits: In cooperation with SutterSelect, we will obtain aggregate claim information for subjects at the intervention and control campuses. The aim of this data is to evaluate differences in health plan costs between the two groups. No individual health claims information will be collected. The data access form will review the security and privacy controls to ensure protections are in place. This data will be collected one year prior to enrollment, the 12-month study period and five years after.

Questionnaires: Subjects will complete all questionnaires remotely using a secure instance of REDCap.

BEVQ: BEVQ is a food frequency questionnaire measuring specific beverage items. We will use an adapted version of the BEV-Q field tested in the UCSF studies that captures beverage consumption while in the workplace and while not at work. The questions ask the type and frequency of consuming specific types of beverages on a typical day: regular/non-diet soda, diet soda, 100% fruit juice, fruit drinks (lemonade, smoothies), sports or energy drinks, sweetened coffee or tea drinks (Arizona iced tea, Frappucinos), and water. Participants also report how much (in ounces) they consume of each beverage each time over a limited, one week, recall period. Daily intake can be calculated for each beverage type by multiplying the frequency and serving size

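### Pregnancy is excluded at entry but neither recorded by name nor given an analysis rule at 6 and 12 months, which adds avoidable noise to the waist and HOMA outcomes

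*Combined protocol and SAP*

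**What the plan says.** Section 4d (Subject Selection) lists a single exclusion criterion, pregnancy. The word appears nowhere else, and no reason for the exclusion is given.

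The procedures table in section 4b repeats Medical History at baseline, 6 and 12 months and describes it as "Self-reported concurrent medications and general medical history with an emphasis on diabetes". The narrative below the table says that "general medical history will be obtained directly from study participants with an emphasis on metabolic history such as diabetes". Neither names pregnancy, and no other scheduled item does.

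Waist is measured at all three visits by the participant: "A tape measure with instructions will be provided to the participant to measure at the designated timepoints". The value is entered by the participant in REDCap. For blood, "Labs will be drawn at baseline and at 12-months".

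Section 1 says that the primary outcomes "are central obesity (e.g., waist circumference) and change in serum insulin sensitivity (homeostatic model assessment [HOMA] ratio"). The secondary outcomes "include changes in SSB consumption, Body Mass Index (BMI), and lab values to include" a list that contains the lipid profile.

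The Aim 1 analytic plan in section 4c states: "We will analyze Aim 1 using all data collected at the baseline, 6- and 12-month time points". The covariates in its example model are the two assignments, baseline HOMA, SSB consumption and BMI, race/ethnicity and sex. The only outlier rule, pruning beyond 4 SD, is written for SSB consumption data.

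Under Medical Record, section 4b also requests Epic data covering the study year: "Medical records data collection will include medication history, progress reports, discharge summaries" and other items.

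**The concern.** Follow-up lasts 12 months in a working-age hospital workforce, so some participants may be pregnant or recently delivered at an assessment. Waist in mid-to-late pregnancy does not measure central obesity, and HOMA in pregnancy does not measure the insulin-sensitivity change that the trial is after. The entry criterion keeps such values out at baseline, but nothing keeps them out afterwards. A late-pregnancy waist would count as a large gain in central obesity.

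A few very large, irrelevant changes widen the variance of a primary outcome. Section 4c also relies on the anthropometric and blood measures as the objective check on self-reported SSB intake, so their interpretability matters for that purpose too. If status is not asked at the visit, identifying these participants later depends on incidental disclosure or on medical records, and the decision on what to do with their values could then be made with outcomes in view.

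**Working it through.** **Does anything in the plan catch these values?**

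- Entry: pregnancy excluded (4d).
- 6 months: waist and weight taken; general medical history, pregnancy not named; no blood draw (4b).
- 12 months: waist, weight and fasting blood taken; same medical history item (4b).
- Analysis: all collected data, no pregnancy term, and an outlier rule for SSB consumption only (4c). Aim 2 reuses the Aim 1 models with an interaction added.

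Nothing does. The exposed values are waist at 6 and 12 months, BMI at 6 and 12 months, and HOMA and lipids at 12 months only.

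**The plan's retained sample.** 700 × 0.80 = 560, or 280 on each side of a main-effect comparison. The plan states 550 (550/700 = 78.6%), or 275 per side. The difference is immaterial here; 280 is used below.

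**Assumptions, none in the documents.** Proportion in mid-to-late pregnancy at 12 months p = 1% or 3%; added waist d = 20 cm; SD of waist change otherwise 6 cm (variance 36); two-sided alpha 0.05; no campus clustering. The 2.1 cm yardstick is the pilot's waist reduction, a before-after change in a study without a non-intervention control group.

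**Formulas.** Added variance = p(1−p)d². SE of the difference = SD × √(2/280). Power = Φ(difference/SE − 1.96).

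- p = 1%: 0.01 × 0.99 × 400 = 3.96
- p = 3%: 0.03 × 0.97 × 400 = 11.64

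| p | Variance | Rise | SD (cm) | SE (cm) | Power, 2.1 cm | Power, 1.5 cm |
|---|---|---|---|---|---|---|
| 0 | 36.00 | – | 6.00 | 0.507 | 98.5% | 84% |
| 1% | 39.96 | 11% | 6.32 | 0.534 | 97.6% | 80% |
| 3% | 47.64 | 32% | 6.90 | 0.583 | about 95% | 73% |

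**Chance imbalance is the same effect.** At 3%, the SD of the difference in pregnancy counts between two groups of 280 is √(2 × 280 × 0.03 × 0.97) = 4.04. That shifts the waist difference by 4.04/280 × 20 = 0.29 cm. The added variance gives the same number: √(2 × 11.64/280) = 0.29 cm. It is one cost seen two ways and must not be counted twice. At 1% it is √(2 × 3.96/280) = 0.17 cm.

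**Wider assumed range** (1-4% pregnant, 10-30 cm added, 275 per side). With an SD of 6 cm, power for 2.1 cm falls from 98% to between 98% and 83%. With an SD of 8 cm, it falls from 87% to between 86% and 70%.

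The documents give no SD or pregnancy effect for HOMA, so no figure is offered for it.

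**The case against.** The strongest reply is that pregnancies may come to light anyway. The repeated history is general, and diabetes is an emphasis rather than a limit. The REDCap form itself is not in the documents. The Epic request spans the study year and includes progress reports and discharge summaries, so a pregnancy or delivery treated within Sutter could be dated afterwards. This stands in part: a reader might infer that the problem cannot be corrected later, and the documents do not support that. But neither source is specified for this use, the completeness of Epic for these employees is not stated, and no rule says what to do once a pregnancy is known.

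Second, a reader might infer that the treatment comparison is biased. Nothing in the documents shows this. Counselling is individually randomised, and no mechanism linking the sales ban to pregnancy is apparent. The standard error already reflects the extra spread, so what is lost is precision and interpretability. For the ban, 8 campuses against 8, stratified only by location and size, could differ in age and sex mix, so balance should be checked; imbalance is possible but not shown.

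Third, the size is assumed, and 3% is towards the high end. If mid-to-late pregnancy lasts about 20 weeks (also an assumption), 3% at one visit implies 3% × 52/20 = 7.8% of all analysed participants passing through it each year, men and older staff included; 1% implies 2.6%. Some would miss the 12-month visit, and 20% attrition is already planned for. This stands and limits the weight of the point.

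Fourth, setting post-randomisation values aside is an estimand choice, and keeping all values as primary with a pregnancy-excluded sensitivity analysis is also defensible. That is fair, but it argues for writing a rule, not for leaving it unwritten.

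**Conclusion.** The gap is real and its likely effect is modest. Pregnancy is screened out at entry, no follow-up item names it, and the analysis plan has no rule for values measured during it. Waist (6 and 12 months) and HOMA (12 months) are the exposed primary outcomes. It would be tempting to add BMI to the primary outcomes or to say that HOMA is affected at 6 months, but BMI is secondary and no blood is drawn at 6 months.

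Under the assumed 1-3% prevalence, 20 cm added waist and 6 cm SD, the variance of waist change rises by 11-32%, and power for 2.1 cm falls from about 98% to 95-98%. The loss is larger where the true effect is smaller: for 1.5 cm, from 84% to 73-80%. These figures ignore campus clustering and illustrate scale only. The point does not threaten the validity of the trial, but it should be settled before follow-up data are collected, because status is most reliably recorded at the visit.

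**What to change.** Add one REDCap item to the 6- and 12-month medical history: currently pregnant, or delivered since the last assessment, with the date. Cross-check it against the Epic extraction where available.

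Add to section 4c, before outcomes are seen, that waist, weight/BMI, HOMA and lipid values taken during pregnancy or within a pre-set postpartum interval are excluded from the primary analysis, with a sensitivity analysis using all values. SSB intake and questionnaires stay in. Report the number of excluded values by arm, and for the sales ban by campus, rather than assuming that they balance.

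The cost is one question, a sentence or two in the analysis plan and a few missing primary values.
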